first half and second half of the trials in block 2, separately. The results are essentially unchanged from those shown in Figure 5. Exposure to Low Prevalence with Feedback in block 1, produces a conservative shift in block 2 criterion in both the first half and the second half of block 2. All t-tests for pairs where Block 1 is Low Feedback are significant except for the Low Feedback → High Feedback pair in the first half, when the effect should be stronger than in the second half. Exposure to High Prevalence with Feedback in block 1, produces a liberal shift in block 2 criterion in both the first half and the second half of block 2. T-tests when block 2 is Low Feedback, Low No Feedback and High No Feedback are significant. T-test when block 2 is High Feedback is not significant in either half (again, recall that the High Feedback -> High Feedback pair has the fewest instances in the dataset).

The lack of any systematic decrease in the magnitude of the effects is shown in Figure 8. The mean change in criterion is plotted for the first and second half of each pair of blocks. Note the grouping of the pairs. The dark blue pairs show the conservative (positive) shift following low prevalence with feedback. The red pairs show the liberal (negative) shift following high prevalence with feedback. If the effects only lasted for the first 2-3 dozen trials, these effects should collapse toward zero in the second half. Clearly, this is not the case.

[figure not shown]

Figure 8: Mean change in criterion for the first and second halves of a block of trials.

Effects of Expertise

As noted in the Methods section, participants gave a rough categorization of their level of expertise. Sadly, this convenience population does not include any substantial number of self-identified expert dermatologists. Only one MD self-identifies as a dermatologist. We can create an expertise continuum from participants reporting no medical training to premedical students to medical students and, finally, to medical doctors. Table 6 shows the numbers of participants and the number of pairs of data contributed by each group.

Expertise category	No. of Participants	No. of pairs
Medical Doctor	54	131
Medical Student	337	952
Pre-Med Student	174	426
No Medical Experience	145	358

Table 6: Number of participants in each expertise group and the number of condition pairs contributed by the groups.

Figure 9 shows d' and criterion as a function of expertise group, regardless of the type of feedback or prevalence (Recall, from Figure 2, that there is little effect of block type on d' .)

[figure not shown]

Figure 9: Effects of expertise category on d' and crit, regardless of prevalence and/or feedback.

There is a highly significant effect of expertise category ($F(3, 1863) = 38.58, p < 0.0001$, partial eta-squared = 0.86) and, as can be seen by the pairwise comparisons, that effect is entirely due to superior performance of the medical students (all comparisons to medical students, $p \leq 0.0001$).

It might seem disappointing that MDs were no better at this task than non-medical participants.

However, these non-dermatologist MDs may not have spent time looking at skin lesions for many years and the novices were only being asked to perform a difficult, but straight-forward, two-alternative, forced-choice discrimination. It is the medical students, many of whom may have recently been learning about skin lesions, who do somewhat better on this task. Of course, there could be other reasons for the group differences (e.g. motivated, competitive students versus more casually interested MDs. We cannot know in this case.)

There is a very modest effect of expertise category on criterion ($F(3, 1863) = 3.32, p = 0.02$, partial eta-squared = 0.01). Pairwise comparisons reveal that premedical students are slightly more conservative than medical students ($p = 0.049$). This does not appear to be a particularly meaningful finding.

In terms of the impact of expertise on the effect of block 1 on block 2, the data are noisy, with fewer pairs showing significant effects of block 1 on block 2. This seems to be a statistical power issue. The pairs that are significant are the same as those seen in Figure 4, with low prevalence on block 1 making participants more conservative on block 2 and high prevalence making them more liberal. There is no evidence for any systematic effect of expertise. In particular, there is no evidence that the most expert group (medical students) shows a different pattern of results. In

that group (fortunately, the largest), Pairs with Low Feedback as block 1 are more conservative and with High Feedback as block 1 are more liberal (all $p \leq 0.01$).

Literature Cited

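### Whether skill alters carry-over is judged only by career stage, which does not order d' in this study, and without an interaction test; the printed effect size of 0.86 should be about 0.058

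*Combined protocol and SAP*

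**What the plan says.** All of this is in the Specific Protocol part of the combined document.

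- **The scale.** Effects of Expertise notes that "participants gave a rough categorization of their level of expertise" and that "Only one MD self-identifies as a dermatologist". It then states: "We can create an expertise continuum from participants reporting no medical training to premedical students to medical students and, finally, to medical doctors". Table 6 gives the pairs per group: MD 131, medical student 952, pre-med 426, no medical experience 358.
- **The scale against d'.** The ANOVA of d' by category is reported as "F(3, 1863) = 38.58, p < 0.0001", with "partial eta-squared = 0.86". The text puts the whole effect down to the medical students and comments: "It might seem disappointing that MDs were no better at this task than non-medical participants".
- **The scale against carry-over.** The within-group results are called noisy, with fewer significant pair types, and this is put down to power. The text then says: "There is no evidence for any systematic effect of expertise". It goes on to treat medical students, not MDs, as the group with the most expertise, and reports that their carry-over follows the overall pattern (all p ≤ 0.01).
- **Where d' is used.** Statistical Analysis / Results computes d' for each block and drops a pair if either member is below 0.5. No section relates d' in block 1 to the criterion change in block 2.

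**The concern.** A moderator analysis needs a moderator that tracks the construct and a test of whether the effect differs across it. Both are weak here.

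The career-stage order does not follow measured skill: its top step does not exceed its bottom step. The one figure suggesting that career stage separates skill well is the 0.86, and it is wrong. A reader who trusts it would think the categories account for most of the variation in d'.

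The statement about expertise also rests on counting significant cells within groups of very unequal size. A smaller group yields fewer significant cells even when its effect is identical. Significance among medical students does not show that their effect equals that of the others.

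The stake is interpretive. The introduction to the Specific Protocol presents these data as new evidence on prevalence effects in expert populations, so readers will take the expertise statement as informative about skill.

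**Working it through.** **1. The stated effect size.** Partial eta-squared = F·df1 / (F·df1 + df2). Applied to all five ANOVAs in the document:

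| Effect | F, df | Computed | Stated |
|---|---|---|---|
| Condition on d' | 6.461; 3, 2076 | 19.38 / 2095.38 = 0.009 | 0.01 |
| Condition on criterion | 30.16; 3, 2076 | 90.48 / 2166.48 = 0.042 | 0.04 |
| Block type on RT | 52.88; 3, 299422 | 158.64 / 299580.64 = 0.0005 | 0.0005 |
| Expertise on criterion | 3.32; 3, 1863 | 9.96 / 1872.96 = 0.005 | 0.01 |
| Expertise on d' | 38.58; 3, 1863 | 115.74 / 1978.74 = 0.058 | 0.86 |

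Four values reproduce to rounding; the fifth does not. The degrees of freedom are sound: 131 + 952 + 426 + 358 = 1,867 pairs, less 4 groups, is 1,863. To reach 0.86 with them, F would have to be (0.86 / 0.14) × (1863 / 3), about 3,815. So about 94% of the variation in observed d' lies within the career-stage groups. Part of that 94% is sampling noise in d', so it is not all unexplained skill.

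**2. The order.** Proposed: none, pre-med, medical student, MD. Reported on d': medical students above each of the other three, and MDs no better than those with no training. The order is not monotone, and the text's own later ranking of medical students as most expert departs from it.

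**3. What the within-group tests can see.** Average cell = group pairs / 16. Power of a two-sided one-sample t-test at 0.05 (noncentral t), for effects in the Cohen's d range of 0.2 to 0.5 reported with Figure 5:

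| Group | Pairs per average cell | d = 0.2 | d = 0.3 | d = 0.5 |
|---|---|---|---|---|
| MD | 131/16 = 8.2 | 8% | 12% | 24% |
| None | 358/16 = 22.4 | 15% | 27% | 62% |
| Pre-med | 426/16 = 26.6 | 17% | 32% | 70% |
| Medical student | 952/16 = 59.5 | 33% | 62% | 97% |

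Cells are uneven (Table 5), so individual cells lie either side of these values. The calculation treats pairs as independent.

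**4. What a continuous measure could see.** Table 5 has 585 pairs with Low Feedback first and 496 with High Feedback first. By Fisher's z, the correlation detectable with 80% power at two-sided 0.05 is tanh(2.80 / √(n − 3)): 0.12 for n = 585 and 0.13 for n = 496. If repeated pairs per participant give a design effect of 2 to 3 (an assumption), these become 0.16 to 0.20 and 0.18 to 0.22. They are slopes within one predecessor type; the difference between two slopes is estimated less precisely.

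**5. Is block 1 d' usable?** The outcome is block 2 criterion minus a baseline for the second-block condition. Block 1 d' comes from other trials, so within a pair the two are not linked arithmetically. It is noisy: with d' = 1.3 and criterion 0.33 as illustrative values, the hit rate is 0.626 and the false-positive rate 0.164. The delta method, √[H(1−H)/(nₛφ_H²) + F(1−F)/(nₙφ_F²)], then gives an SD of 0.37 for 16 targets and 64 non-targets, and 0.31 for 40 and 40.

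**The case against.** The other side has several good points.

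- **The text is measured.** It reports an absence of evidence and admits limited power; it does not assert that expertise has no effect. A reader might infer that it claims a proven null, but it does not.
- **The text adapts to its d' result.** It offers reasons why MDs did not do better and checks medical students separately. The ANOVA spends 3 degrees of freedom, so the groups are compared as nominal categories and the comparison stays valid even though the order fails.
- **Career stage is not the only moderator examined.** Delay between blocks and half of block 2 are also studied. It is the only one related to skill.
- **The categories could test direction.** Medical students against the rest is 952 against 358 + 426 + 131 = 915 pairs, a nearly balanced contrast of higher with lower d'. What is missing is the interaction test, which could have been run on the existing groups.
- **Block 1 d' is imperfect.** It is measured during the exposure block, and condition affects d'. Its precision differs by prevalence, so attenuation differs slightly between the two slopes being compared. The 0.5 filter was applied because motivation could not be controlled; without it, low d' partly reflects low effort.

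All of this stands. It limits what the added model can show and is a reason to report both moderators. It does not supply the missing interaction test or rescue the 0.86.

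The text also says that removing the filter leaves the pattern unchanged. That shows robustness to adding low-d' pairs; it does not test whether carry-over varies with d'.

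**Conclusion.** The point holds as an inexpensive improvement to a secondary analysis. Three things follow from the document itself. Career stage does not order d'. Its effect size on d' is about 0.058, not 0.86. The statement on expertise rests on within-group significance with no reported interaction test, and average cells run from about 8 to 60 pairs. The power figures assume independent pairs spread evenly over 16 cells.

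Three stronger readings are not supported.

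- A reader might infer that more skilled observers do carry over less. The pair-level data are not in the document, so the result cannot be computed here in either direction.
- A reader might take the ideal criterion shift between 50% and 20% prevalence, ln(4)/d', to predict half the carry-over at twice the d'. That formula describes adjustment to a known prevalence in the current block. Prevalence was not announced to participants, and carry-over concerns the previous block.
- A reader might quote a fixed gain in information from using block 1 d' in place of career stage. Any such figure depends on the reliability of a single block's d', and the document does not give the between-person SD needed to find it.

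The main finding on criterion after feedback blocks does not depend on this analysis.

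**What to change.** 1. Correct the partial eta-squared for expertise on d' to about 0.06, or correct the F if that is what was misprinted.
2. Add a mixed model for block 2 criterion with block 1 condition, block 2 condition, block 1 d' (continuous), the interaction of block 1 d' with predecessor type (Low Feedback versus High Feedback), and a participant random effect, because participants contribute up to 24 blocks.
3. Run it on the pairs that pass the d' > 0.5 filter and again on all complete pairs, and show both.
4. Beside it, report the interaction of career stage with predecessor type, or the simpler contrast of medical students with the rest.
5. Base the statement about skill on these interaction estimates and their confidence intervals, and describe the category result as a comparison of career stages.
6. State the limits of block 1 d': it is noisy, to a different degree in low and high prevalence blocks; it is measured during exposure; and without the filter it mixes effort with skill.

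The cost is a small amount of extra modelling on data already held, a corrected figure and a few reworded sentences. The new model should be labelled exploratory, since it is added after the results were seen.

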Data were collected on-line via a free and open iOS application, “DiagnosUs”, created by Centaur Labs as a platform for game-like image labeling competitions <https://www.centaurlabs.com/>). Between 6/22/21 and 6/27/21, Centaur Labs ran 24 ‘contests’ on our behalf, collecting >300,000 trials from 803 participants in 6 days. Each of the 24 contests consisted of 80 unique images of a skin lesion as shown in Figure 1. This is a relatively small number of images, but it kept the sessions short and encouraged participation. Images came from the International Skin Imaging Collaboration (ISIC) 2018 challenge (Codella, et al., 2019). The set contains over 1,200 melanoma images and over 7,600 nevus images.

[figure not shown]

Figure 1: Sample stimulus displays. Left: Participants are asked if a lesion is a melanoma (cancer) or a nevus (benign ‘mole’). Right: After response, if this were a feedback condition, red or green feedback would inform the observer of the correctness of the answer. In no feedback conditions, neutral feedback indicated that the response had been registered.

On each of the six days, there were four contests available. These were:

- 1) Low Prevalence – No Feedback; consisting of 20% (16) melanoma images
- 2) Low Prevalence – Feedback; prevalence was the same as in #1, but with accurate, trial by trial feedback
- 3) High Prevalence – No Feedback; consisting of 50% (40) melanoma images
- 4) High Prevalence – Feedback; prevalence was the same as in #3, but with accurate, trial by trial feedback

The contests were randomly assigned to participants with the constraint that they did not run the same type of contest more than once in a day. Participants could take part in as many or as few contests as they wished over the course of the six days and they could end up repeating a

condition from one day on another day. The prevalence and feedback conditions were not advertised to participants. Accuracy is the main dependent variable though we also collected response times.

Because of the on-line, voluntary nature of the data collection, we did not have control over the viewing conditions or the type of screen used. We compensated by collecting a very large dataset (see below).

Observers

We collected data from 803 unique individuals. For each individual, we have a crude categorization of expertise as shown in Table 1:

Medical Student	337
Pre-Med Student	174
No Medical Experience	145
Medical Doctor	54
Other Healthcare Professional	47
Nurse	25

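### The expertise ANOVA on d' counts 1,867 block pairs as independent, and the text gives no estimate or interval for its claim that MDs had no advantage over novices

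*Combined protocol and SAP*

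**What the plan says.** In the Combined protocol and SAP, the Effects of Expertise section of the Specific Protocol compares d' across four groups: MDs, medical students, pre-medical students and people without medical experience. The omnibus result reads: "There is a highly significant effect of expertise category ($F(3, 1863) = 38.58, p < 0.0001$, partial eta-squared = 0.86". The section then says "that effect is entirely due to superior performance of the medical students", and gives p of 0.0001 or less for every comparison with that group. The next paragraph states: "It might seem disappointing that MDs were no better at this task than non-medical participants". It goes on to suggest why MDs might not do well on this task.

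Table 6 lists participants and then pairs for each group, among them "Medical Doctor 54 131" and "No Medical Experience 145 358". The printed text gives no difference, interval, p-value or margin for MDs against people without medical experience.

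**The concern.** Two things go wrong together.

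First, the unit of analysis. Level of training is a fixed attribute of a person, but the ANOVA takes each pair of blocks as a separate observation. The Observers section says that some people ran 24 blocks and others 2. Repeated pairs from one person resemble each other, so the pair count overstates how much is known about the group.

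Second, the wording. Medical students beating every other group does not show that the other three groups are equal. To give students the whole effect, and to say that MDs had no advantage, one needs evidence on the MD-minus-novice difference itself. The text offers none, yet builds an explanation on its absence. If MDs were moderately better than novices, a reader would carry away the wrong message about clinical training and this task.

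**Working it through.** **Inputs.** Participants and pairs from Table 6: MDs 54 and 131; no medical experience 145 and 358; medical students 337 and 952; pre-medical students 174 and 426. Assumptions not in the documents: two-sided alpha 0.05, equal group SDs, normal approximation, and a within-person correlation (ICC) of 0.2 to 0.8.

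**1. Reproducing the plan's figure.** 131 + 952 + 426 + 358 = 1,867 pairs, and 1,867 − 4 = 1,863, the printed error degrees of freedom. The unit is the pair. (Separately, the F value implies a partial eta-squared of 3 × 38.58 / (3 × 38.58 + 1,863) = 115.74 / 1,978.74 = 0.058, not 0.86. That is a different reporting error and does not affect this point.)

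**2. How many MDs?** The four head counts in Table 6 equal those in Table 1, which describes the full sample: "We collected data from 803 unique individuals". The pairs come after three exclusions: people without a full block (803 down to 630), people with a single block, and pairs in which either d' was below 0.5. So 54 is a ceiling. The number of MDs who supplied the 131 pairs is not stated.

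**3. Precision.** The 95% half-width is 1.96 × √(1/n₁ + 1/n₂).
- Pairs as independent, 131 v 358: 1.96 × 0.102 = 0.20 SD of pairs.
- People, 54 v 145: 1.96 × 0.159 = 0.31 SD of person means.

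The two SDs are not the same unit. To stay in pair SDs, inflate each group's variance by 1 + (m − 1) × ICC, with m = 131/54 = 2.43 and 358/145 = 2.47. The half-width is then 0.23 at ICC 0.2 and 0.29 at ICC 0.8. This assumes that everyone listed contributed equally; unequal contributions widen it further.

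**4. Power.** Φ(δ/SE − 1.96), with SE = √(1/n₁ + 1/n₂).
- 54 v 145, δ = 0.5: Φ(3.14 − 1.96) = 88%.
- 54 v 145, δ = 0.3: Φ(1.88 − 1.96) = 47%.
- 131 v 358 pairs, δ = 0.5: 99.8%, which is what the pair count suggests.

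**5. What non-significance would show.** At 54 v 145, the upper limit is the observed difference plus 0.31. An advantage of 0.5 SD is excluded if the observed difference is below 0.5 − 0.31 = 0.19 SD. A difference just short of significance would have an upper limit of about 2 × 0.312 = 0.62 SD.

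**6. If fewer MDs contributed.** These head counts assume that MDs and novices were lost at the overall rate, which is not documented.

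| MDs v novices | Basis | 95% half-width | Power, 0.5 SD |
|---|---|---|---|
| 54 v 145 | Table 6 as listed | 0.31 | 88% |
| 42 v 114 | × 630/803 | 0.35 | 79% |
| 21 v 57 | × 315/803, where 315 = 630 − 315 single-block people | 0.50 | 50% |

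The last row is rough: it uses the single-block row of Table 4, and that table sums to 872 people, not 630. If a Šídák level for six comparisons were used (1 − 0.95^(1/6) = 0.0085), 54 v 145 would give a half-width of 0.42 and 69% power. Šídák is named for the condition ANOVA, not for expertise.

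**The case against.** - **Figure 9 is not available.** The text refers the reader to pairwise comparisons there, and several other figures carry means with 95% intervals. The missing numbers may be in it. This stands: the gap can be asserted only of the printed text, and the non-significance of MDs against novices is itself inferred. If the MD mean was at or below the novice mean, the remark may simply describe the sample. A pair-level interval in the figure would still have the wrong unit.
- **Unequal contributions are addressed.** The Observers section says that the main analyses were repeated on each person's first pair and kept their pattern. But the expertise section reports no such repeat, and a check that significant effects persist does not support a claim of no difference.
- **A reader might infer that there were too few MDs to exclude a 0.5 SD advantage.** The documents do not support that. At the only documented head counts, power is 88% and the half-width is 0.31 SD. Smaller head counts rest on assumed attrition, and the lowest also on a table that does not reconcile.
- **A reader might infer that ranking medical students as the most expert group depends on the MD null.** It does not. It rests on students beating every group, MDs included. For MDs, p = 0.0001 on the pair analysis implies at least 3.89 × √(1/131 + 1/952) = 0.36 pair SD.
- **The analysis is secondary and hedged.** The text calls the expertise categories crude and admits other explanations for the group differences. This limits the severity but does not supply the missing estimate.

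**Conclusion.** The point holds in a limited form. That the ANOVA ran on pairs is certain from the degrees of freedom. That its p-values are too optimistic is likely, and by how much depends on an undocumented within-person correlation. The equality wording has no estimate or interval behind it in the printed text. Even if all 54 MDs contributed, the person-level half-width is about 0.31 SD, and a 0.3 SD advantage would be missed slightly more often than found (power 47%). Fewer contributing MDs would widen the interval. Whether 0.5 SD, or any other advantage, is excluded cannot be decided without the observed difference. The direction of the student advantage and the main carry-over finding on criterion are not in question here.

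**What to change.** Re-run the expertise comparison with one mean d' per participant, or with a participant random intercept on the block data. Report two differences with 95% confidence intervals: MD minus No Medical Experience, and MD minus Medical Student. State how many MDs, and how many people in each other group, supplied the analysed pairs. Reword the two sentences to say that no MD advantage over novices was detected and that advantages larger than the upper limit are excluded. Keep the equality wording only if that limit is below a margin that the text states and justifies.

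The cost is one re-analysis of existing data and two rewritten sentences. The intervals will be wider and the conclusion of this secondary analysis weaker.

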each of these effects, we derive measures of d' and criterion for each of the 16 pairs (combinations of one of four 'first blocks' with one of four 'second blocks'). We then subtract a baseline derived from all blocks of the second block condition. We use the second blocks as the baseline because we are looking for a change in the second block. In fact, it doesn't make much difference. Many second blocks in one pair are the first blocks in a subsequent pair and the baselines would be very nearly the same if all blocks were included as in Figure 2 above. Thus, for example, to assess the influence on criterion of Low Prevalence without Feedback (Condition 1 in the figures to follow) on High Prevalence without Feedback (Cond 3), we compute $\text{Criterion}(\text{pair 13}) - \text{Criterion}(\text{Cond 3})$. This is done for each of the 2080 pairs of blocks using the $d' > 0.5$ filter. The data for each of these 2080 "good" pairs of blocks are posted on the Open Science Framework at <https://osf.io/hck5n/>.

Figure 4 shows the change in D' as a function of pair with each dot representing one pair of blocks. Statistical tests are simple T-tests against a null hypothesis of no change in d' from block 1 to block 2. Three pairs, forming no obvious pattern, reach statistical significance (all $p = \sim 0.02$, all Cohen's $d = \sim 0.2$). As these are not corrected for multiple comparisons, these should not be considered strong effects. The general picture is of little or no effect of the first block of trials on d' in the second block of trials.

[figure not shown]

Figure 4: Change in d' on block 2 as a function of the nature of block 1. X-axis gives numerical values for each member of a pair where 1 = low prevalence, no feedback, 2 = low prevalence, with feedback, 3 = high prevalence, no feedback, and 4 = high prevalence, with feedback. P-values show results for simple t-tests, testing against the null hypothesis that there is no change in d' . Black lines show means +/- 95% confidence intervals.

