A different pattern is seen in the criterion data, plotted in Figure 5. Here, there are two clear clusters of significant effects. When block 1 has low prevalence and feedback, criterion on block 2 is more conservative (Pairs where Block 1 is low prevalence with feedback, all $p < 0.006$, Cohen's d between 0.2 and 0.5). When block 1 has high prevalence and feedback, criterion on block 2 is more liberal (Pairs where Block 1 is high prevalence with feedback, $p < 0.0005$, pair

44, $p = 0.017$; note that there are only 27 pairs of this variety in the dataset, All Cohen's d between 0.2 and 0.5). When block 1 does not have feedback, there is no effect on criterion in pair 2, except, perhaps, for 'high feedback' on Block 2 ($p < 0.028$, again, not corrected for multiple comparisons, Cohen's $d = 0.18$). This is the main finding of the paper. Criterion can be manipulated by the prevalence of the preceding block of trials, but only if the participants received feedback on that first block.

[figure not shown]

Figure 5: Change in criterion on block 2 as a function of the nature of block 1. P-values
show results for simple t-tests, testing against the null hypothesis that there is no change in
criterion. Black lines show means +/- 95% confidence intervals.

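### The expertise subgroups have no stated baseline; if the pooled one was kept, each group's own criterion offset is counted as part of its carry-over

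*Combined protocol and SAP*

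**What the plan says.** The change score is defined in the Specific Protocol, under How does one block influence the next? For each of the 16 ordered pairs of conditions: "We then subtract a baseline derived from all blocks of the second block condition". The scope is stated as "This is done for each of the 2080 pairs of blocks" that pass the d' filter. Nothing in that definition separates participants or expertise groups. The scores are tested cell by cell with simple t-tests, described under Figure 5 as "testing against the null hypothesis that there is no change in criterion". For first blocks with low prevalence and feedback, the whole-sample result is "all $p < 0.006$, Cohen's d between 0.2 and 0.5". The effect after high prevalence with feedback is in the opposite direction, with the same range of Cohen's d.

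The Effects of Expertise section does two things. It compares criterion between four expertise groups: "There is a very modest effect of expertise category on criterion", with F(3, 1863) = 3.32, p = 0.02, and then "Pairwise comparisons reveal that premedical students are slightly more conservative than medical students", p = 0.049. It sets this difference aside as not very meaningful. It then reports the effect of block 1 on block 2 by group. Fewer pairs are significant, which is put down to power. Medical students show both shifts with all p at or below 0.01. The conclusion is "There is no evidence for any systematic effect of expertise". No baseline is named for this analysis, and no test of group by predecessor is reported.

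**The concern.** A one-sample test against zero is a clean test of carry-over only if the subtracted baseline is what the same people would show without a particular predecessor. With a baseline averaged over everyone, a group that is habitually more conservative has a positive mean change even with no carry-over. If that offset is constant across conditions, it has one sign in every cell. In a conservative group it adds to the conservative shift after Low Feedback and subtracts from the liberal shift after High Feedback. In a liberal group it does the reverse.

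The section argues about expertise from which subgroup cells reach significance. That evidence is exposed to the offset, because the offset changes the balance between the two sets of cells in each group. What is at stake is the comparison across groups, not the main finding of the study.

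**Working it through.** **Inputs.** Pairs per group come from Table 6: MD 131, medical student 952, pre-med 426, no medical experience 358. Cell counts come from Table 5 (2,080 pairs). F = 3.32 and p = 0.049 come from Effects of Expertise, and carry-over d of 0.2 to 0.5 from the text on Figure 5.

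**Reproducing the stated test.** 131 + 952 + 426 + 358 = 1,867 pairs, less 4 groups, gives 1,863 error df, as stated. F = 3.32 on 3 and 1,863 df gives p = 0.019 (stated 0.02). Partial eta-squared = 3F/(3F + 1863) = 9.96/1872.96 = 0.005 (stated 0.01).

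**Gap between pre-meds and medical students.** Gap = t × sqrt(1/426 + 1/952), in within-group SDs. The text does not say whether p = 0.049 is adjusted.
- Unadjusted: t = 1.970, gap = 0.115 SD.
- Šídák over six comparisons: single-test p = 1 − (1 − 0.049)^(1/6) = 0.0083, t = 2.641, gap = 0.154 SD.

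**Offsets from the pooled mean.** The simple case puts the other two groups at the pooled mean. Then 426b = 952a with a + b = gap, so b = gap × 952/1378 and a = gap × 426/1378. Pre-meds are 0.079 to 0.106 SD conservative and medical students 0.035 to 0.048 SD liberal.

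Without that assumption, the between-group sum of squares in SD units is fixed at 3 × 3.32 = 9.96. Searching all positions of the other two groups that satisfy it together with the gap gives:
- gap 0.115: pre-meds 0.045 to 0.114 conservative; medical students 0.001 to 0.070 liberal
- gap 0.154: pre-meds 0.082 to 0.130 conservative; medical students 0.024 to 0.072 liberal

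Overall, this is about 0.05 to 0.13 SD for pre-meds and 0.00 to 0.07 SD for medical students.

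**Effect on pre-med cells.** Cell sizes are taken as Table 5 count × 426/2080. After Low Feedback, 140, 110, 117 and 218 become 29, 23, 24 and 45. After High Feedback, 134, 218, 117 and 27 become 27, 45, 24 and 6. The chance of significance in the expected direction is the upper tail of the noncentral t with n − 1 df and noncentrality (d + b)√n after Low Feedback, or (d − b)√n after High Feedback, beyond the two-sided 5% cut-off. Summed over four cells each, with b = 0.079 to 0.106:

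| True d | After Low Feedback: no offset → with offset | After High Feedback: no offset → with offset | Total of 8 |
|---|---|---|---|
| 0.2 | 0.7 → 1.3-1.5 | 0.6 → about 0.3 | 1.4 → 1.6-1.7 |
| 0.35 | 1.8 → 2.4-2.6 | 1.5 → 0.9-1.0 | 3.3 → 3.5 |
| 0.5 | 2.9 → 3.3-3.5 | 2.4 → 1.8-2.0 | 5.4 → 5.3 |

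With the wider offsets of 0.05 to 0.13, the split at d = 0.2 is 1.1-1.6 and 0.4-0.2, and at d = 0.5 it is 3.2-3.6 and 2.2-1.7.

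**Effect on medical students.** Scaling by 952/2080, the feedback-predecessor cells hold about 12 to 100 pairs. Reaching p = 0.01 then needs an absolute d of about 0.26 (100 pairs) to 0.90 (12 pairs), far above an offset of at most 0.07.

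**The case against.** The strongest reply has four parts.

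First, the expertise section does not say which baseline it used. A reader might infer that the subgroup scores were certainly taken against the pooled mean. The documents do not establish that. It is the natural reading, because no other baseline is defined, but it remains an inference. This stands, and the point is conditional on it.

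Second, a reader might infer that the offset undermines the power explanation. It does not. With no offset at all, a d of 0.2 gives only 1.4 of 8 expected significant pre-med cells, and the offset moves that total to 1.6-1.7. Small cells account for most of the missing significance, as the text says. This stands.

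Third, a reader might infer that pre-meds could seem to show only one half of the effect, or that a real group difference is concealed. At d = 0.5 the expected split with the offset is 3.3-3.5 against 1.8-2.0, so both halves remain visible. A constant offset also cancels when Low Feedback and High Feedback predecessors are compared for the same block 2 condition. Neither inference is supported.

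Fourth, the medical-student result is safe. An offset of one sign cannot produce shifts in opposite directions, and a liberal offset would weaken the conservative shift that is reported as significant. This stands.

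What the reply does not answer is that no within-group contrast of predecessors is reported. Each cell is tested against zero, so the cancellation is not used, and the statement about expertise rests on cell-by-cell significance.

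**Conclusion.** The point holds as a limited one. The documents define only a pooled baseline and report that criterion differs by expertise. If that baseline was kept, each subgroup test carries an offset of about 0.05 to 0.13 SD (pre-meds) or 0.00 to 0.07 SD (medical students), against carry-over of 0.2 to 0.5 SD. The offset makes a symmetric effect look lopsided in pre-meds and barely alters the number of significant cells. It leaves the medical-student result, the power explanation and the whole-sample result in Figure 5 intact.

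The sizes rest on several assumptions:
- Pairs are independent, as in the plan's own ANOVA.
- Subgroup cells are proportional to Table 5.
- The group offset is constant over conditions; the section reports only a main effect.
- The SD behind the group comparison is close to the SD within cells.
- The pooled mean is that of the 1,867 pairs in four groups, although the actual baseline also includes the other 2,080 − 1,867 = 213.

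Corrected subgroup estimates cannot be computed, because no subgroup means or SDs are given.

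**What to change.** State which baseline the expertise analysis used. Then fit one model of block 2 criterion with block 2 condition, predecessor, an expertise main effect and an expertise-by-predecessor term. Base the sentence on expertise on that interaction, with its interval, and not on which cells are significant.

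An alternative is to subtract the mean for the same expertise group and block 2 condition. This is not equivalent to the additive expertise term. It also allows group-by-condition differences, and it is noisier in small groups: 131 MD pairs over four conditions is about 33 per baseline.

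After either change, restate the per-group cells. In the same paragraph, cite Figure 5 (criterion) in place of Figure 4 (d').

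The cost is a rerun on data already held, plus a few sentences of text. The pair-level data are described as posted; if the posted file does not carry expertise labels, they must be linked first.
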